5.4.1 Important Protocol Deviations Leading to Exclusion from the PPS Analysis

Only those deviations considered to have a major effect on efficacy will lead to complete exclusion of the subjects from the PPS population. For the purposes of this study, the following criteria have been identified as important protocol deviations as it is considered that the occurrences of any of these criteria might have an important influence on the primary efficacy endpoint. Other deviations not specifically identified here may result in exclusion from the PPS analysis and will be identified prior to final database lock and unblinding.

Type	Deviation	Method of Identification
Inclusion and Exclusion (I/E) Criteria	Subjects who fail to comply with key I/E criteria	
Programmatic check to identify subjects based on protocol deviations and CRF data who failed to meet the following major eligibility criteria:
 
Exclusion Criteria (additions to the exclusion criterion specified in the protocol are marked in italics):
 
 1. Known history of HIV. 2. Prior liver transplantation. 3. Other well-documented causes of active chronic liver disease, including, but not restricted to: history of positive hepatitis B surface antigen (HBsAg) or HCV RNA (subjects must be viremia free for a minimum of 2 years), suspicion of drug-induced liver disease, alcoholic liver disease and auto-immune hepatitis, Wilson’s disease hemochromatosis, primary biliary cirrhosis, primary sclerosing cholangitis, genetic hemochromatosis, known or suspected HCC, history of planned liver transplant or current MELD score > 12. 4. History of cirrhosis and/or hepatic decompensation including ascites, hepatic encephalopathy or variceal bleeding. Platelet count < 100,000/μL of blood at Screening. 5. AST or ALT >5 times the upper limit of normal at Screening. 8. History of alcohol abuse or drug abuse within 6 months of Screening or discovery of heavy alcohol use during study treatment. 12. Current use of any diabetes medications other than metformin, GLP-1 agonists, SGLT2 inhibitors, sulfonylureas or DPP4 inhibitors three months prior to the baseline diagnostic liver biopsy or during the study unless as specified in the protocol. Current use of insulin or PPARγ agonists (pioglitazone or rosiglitazone) is not allowed for the duration of the study. 21. Participation in an investigational study (other than a non-treatment registry study) or received an investigational drug within 30 days or 5 half-lives (whichever is longer) prior to or any time after randomization. 
Inclusion Criteria:
 
 2. Histological evidence of NASH, based on the central read of the biopsy for purposes of determining eligibility, with a NAS (NASH CRN scoring) ≥ 4 with a score of at least 1 in each component of NAS. 3. Histological evidence of liver fibrosis defined as NASH CRN System fibrosis score of F1 to F3.

Statistical Analysis Plan

Version: Final 1.5

Date of Issue: 16-May-2019

Cirius Protocol No. MSDC-0602K-C009NASH

Type	Deviation	Method of Identification
		
Thus, subjects will be reviewed for exclusion if NAS < 4, or score of 0 in any component of NAS, or fibrosis score of F0 or F4.
 
5. Subjects with type 2 diabetes mellitus (DM) must be under stable and reasonable control, defined as under a healthcare provider's care for DM with glycosylated hemoglobin [HbA1c] ≤ 9.5%. Subjects taking permitted anti-diabetic therapies (metformin, GLP-1 agonists, SGLT2 inhibitors, sulfonylureas or DPP4 inhibitors) must be on stable doses for a period of at least 3 months prior to randomization.
 
Manual review will be performed for identifying subjects who violate the above I/E criteria, including review of prohibited changes reported for the 3 months prior to randomization (in reference to inclusion criterion #5 above).

Prohibited Medication Use	Subjects who took medications that are not permitted during the study	
Programmatic identification of subjects with CRF-reported post-randomization use of PPARγ agonist, insulin, ursodeoxycholic acid, paclitaxel, phenytoin, warfarin, celecoxib, tolbutamide or repaglinide; and subjects with reported protocol deviations related to prohibited medication use.
 
Manual review of blinded concomitant medications listing to identify subjects with prohibited changes post-randomization in therapeutic agents for diabetes. The medical monitor and Sponsor will review the listing and note any prohibited changes in these glycemic control medications; these subjects may be excluded from the PPS.

Non-compliance During the Study	Subjects who had low study drug exposure and compliance	
Programmatic check of estimated compliance based on the study drug administration data, and programmatic identification of subjects assigned to an active treatment group with parent drug (MSDC-0602K) or MSDC-0597 (major metabolite) trough levels below the detection threshold at two or more visits.
 
Manual review will be performed to identify subjects with compliance less than 80% based on study drug administration data (Section 7.7.2) and/or other compliance issues identified by sponsor.

Errors in Treatment Allocation	Subjects who received a wrong treatment at 1 or more study visits due to packaging or dispensing errors during the study	
Programmatic check based on unblinded IXRS database after the study is unblinded for the final analysis. The check will be done by comparing the bottle number that IXRS had assigned to the subject/visit against the bottle number actually used.

Type	Deviation	Method of Identification
Other Significant Protocol Deviation	Protocol deviations based on the clinical monitoring.	Manual review: This list will be reviewed by the medical monitor and Sponsor and important protocol deviations leading to exclusion from the PPS will be identified.

As defined in the table, the majority of the protocol deviations will be determined programmatically from the data. Those criteria that require clinical interpretation will be reviewed prior to final database lock, following discussion with the medical monitor and Sponsor.

All important protocol deviations occurring during the study will be reviewed and approved by the Sponsor prior to final database lock and unblinding for the final analysis. Should other categories of important protocol deviations, not anticipated at the time of preparing this SAP be identified during the study (and prior to unblinding for the final analysis), they will be provided in a separate document and included in all relevant protocol deviation reviews and approvals.

6 DATA HANDLING

6.1 Time points and Visit Windows

Study Day 1

Study day 1 is defined as the date of the first dose or the date of randomization for subjects who were not administered any dose of study drug.

Study Day

Study days after study day 1 are calculated as (assessment date – study day 1 date) + 1. Study days prior to study day 1 are calculated as (assessment date – study day 1 date). The day prior to study day 1 is study day -1, there is no study day 0.

Scheduled and Unscheduled Visits

For the purpose of statistical analysis, the nominal visit designations as assigned by the investigator will be used. Unscheduled visits will be programmatically assigned to a nominal visit designation according to the following definition of visit windows.

Definition of visit windows to assign unscheduled visits to nominal visit designations

Nominal Visit	Target Day (Study Day)	Parameter measured at all visits	Parameter measured at all visits except Visit 8	Parameter measured at all visits except Visits 2, 3, and 8	Parameter measured at Visits 1, 5, 7 and 8	Parameter measured at Visits 1, 5, and 7	Parameter measured at Visits 1 and 7
1 Baseline	1	≤1	≤1	≤1	≤1	≤1	≤1
2 Month 1	30	2-45	2-45	--	--	--	--
3 Month 2	60	46-75	46-75	--	--	--	--

Statistical Analysis Plan

Version: Final 1.5

Date of Issue: 16-May-2019

Cirius Protocol No. MSDC-0602K-C009NASH

4 Month 3	90	76-135	76-135	2-135	--	--	--
5 Month 6	180	136-225	136-225	136-225	2-270	2-270	--
6 Month 9	270	226-315	226-315	226-315	--	--	--
7 Month 12	360	316-367	≥316	≥316	271-367	≥271	≥271
8 Follow-up	374	≥368	--	--	≥368	--	--

For all populations, multiple visits for a given parameter with the same nominal visit designation will be dealt with as follows:

- If both scheduled and unscheduled visit data are available, the scheduled visit data will be used for analysis with the exception of baseline, where the baseline value will be defined as the last scheduled or unscheduled value collected on or prior to the date of the first dose of treatment (or randomization for subjects who were not administered any dose of study drug).
- If multiple unscheduled visits occur within the same visit window and no data from a scheduled visit is available for the corresponding nominal visit designation, then the unscheduled visit closest to the corresponding target day will be used in the analysis. If there is a tie, the later unscheduled visit will be used in the analysis.

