6.5 Liver Function Tests

If subjects demonstrate an increase in AST, ALT or total bilirubin (TB) greater than 2 times their baseline values (mean of Screening & Visit 1), there should be repeat tests of transaminases (AST and ALT), bilirubin, and physical exam performed within 48-72 hours. If the levels then decrease, the subjects will be under close observation (repeat testing 2-3x weekly) until the levels return toward the individual's baseline values. Should these levels continue to be elevated, the drug should be discontinued.

Subjects should be discontinued for elevations of transaminases (AST or ALT) or TB above baseline associated with symptoms of right upper quadrant abdominal pain, fatigue, anorexia, nausea or vomiting, or eosinophilia. Subjects should be discontinued for persistent (> 1 month) increases of AST and ALT and/or TB > 2 times baseline.

Subjects may be rechallenged with study drug and closely monitored with repeat testing at least weekly. Re-elevation of values after re-challenge necessitate permanent discontinuation of study drug (but continuation of study visits).

If a new concomitant medication with known hepatotoxicity is started and liver function tests rise to meet the above criteria, the known hepatotoxin should be discontinued (replaced) if possible and liver function tests be followed in the same manner as outlined above. If liver function tests remain elevated or increase further, then the study drug should be discontinued (and subjects should continue with the study visits).

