6.6 PT/INR Tests

If subjects demonstrate an increase in PT or INR > 2 times the baseline value (mean of Screening & Visit 1), repeat tests of PT or INR and eosinophil counts should be performed within approximately 48-72 hours. If the PT or INR elevation is associated with changes in liver biochemistries, the subject should be followed closely per Investigator judgement with repeat testing at least weekly until levels return toward baseline values. Subjects should be discontinued

from study drug (and continue with study visits) and be referred for treatment if they show signs of spontaneous, serious or persistent bleeding.

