7.5 Efficacy and Pharmacokinetic Assessments

For all subjects, blood samples for pharmacologic (efficacy and safety) assessments will be drawn at all visits except Screening (Table 1). All blood samples should be drawn in a fasted state (approximately 10 hours). Instructions for collecting, processing, storing and shipping of blood samples for pharmacologic and pharmacokinetic analyses will be provided in the Laboratory Manual.

Blood samples for trough PK analysis of MSDC-0602 and MSDC-0597 will be collected pre-dose at Study Visits 2, 4, 5, 6 and 7 (Days 30, 90, 180, 270 and 360).

Blood samples for analysis of FPG and HbA1c will be collected at Screening.

Blood samples for analysis of insulin, HOMA-IR, FPG, HbA1c, TG, FFA and fasting cholesterol (total, HDL, LDL, VLDL) will be collected as part of the standard chemistry profile at Study Visits 1, 5, and 7 (Days 1, 180 and 360).

Blood samples for analysis of liver function tests (AST, ALT, bilirubin, PT/INR, ALP, GGT and albumin) will be collected at Study Visits 1, 2, 3, 4, 5, 6 and 7 (Days 1, 30, 60, 90, 180, 270 and 360).

Blood samples for analysis of HMW adiponectin, hsCRP, osteocalcin, serum CTX concentrations will be collected at Study Visits 1, 5, and 7 (Days 1, 180, and 360).

Blood samples for biomarkers of liver apoptosis (CK-18 [M30 and M65]) will be collected at Visits 1, 5 and 7 (Days 1, 180, and 360), whereas blood samples for TIMP-1, PIIINP, HA will be collected at Visits 1 and 7 (Days 1 and 360).

Serum samples for NMR analysis of lipoprotein particle size will be collected at Study Visits 1 and 7 (Days 1 and 360).

Blood samples will be collected at Visit 1 (Day 1) to be analyzed for genotyping.

Plasma samples for future miRNA measurements and additional biomarkers of interest will be collected at Study Visits 1, 5 and 7 (Days 1, 180 and 360).

Data obtained from the circulating liver function tests and other biomarkers will be used to calculate composite scores that may provide an indirect measure of changes in fibrosis from baseline to the 12 month endpoint (Days 1 and 360).

It is estimated that approximately 226 mL of blood for the safety, pharmacokinetic, and pharmacodynamic parameters will be drawn from each subject who completes the trial.

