7.8.4 Exploratory Analysis

Exploratory efficacy endpoints are listed in Section 3.3.

The analysis of mean change from baseline at 12 months in liver stiffness will be restricted to subjects for whom liver stiffness has been measured using the FibroScan device. The type of device for each subject and time-point was not recorded in the eCRF but will be captured in an external spreadsheet and provided by the Sponsor prior to unblinding for the final analysis.

All exploratory analysis will be performed for the mITT population. For change from baseline endpoints, baseline values, post-baseline values, and change from baseline will be summarized by treatment groups at each evaluation time point. Highly skewed variables will be log-transformed for analysis, and geometric mean changes presented. Comparisons between each active dose and placebo will be done using ANCOVA models for continuous variables, similarly as for secondary endpoints (refer to Section 7.8.2). Regardless of skewness, summaries and ANCOVA results will be presented for log-transformed values of ALT, AST, ALP, and GGT, in addition to results based on non-transformed values.

Fibrosure numeric results (rather than results expressed as fibrosis stage) will be analyzed. Changes in diagnostic category (NASH diagnosis confirmed or cannot be confirmed) from baseline to month 12 will be presented by means of a shift table.

Changes in markers of insulin sensitivity (HOMA-IR, HbA1c, fasting plasma glucose, and fasting insulin) will be analyzed overall and then separately in subjects with T2DM, and in subjects with T2DM without a major up- or down-titration in glycemetic control medications during the study (categorized into the “no major change” category during blinded adjudication).

Mean change from baseline with standard error bars will be plotted for each treatment group by visit for insulin sensitivity markers (HOMA-IR, HbA1c, fasting plasma glucose, and fasting insulin) in the mITT population for (1) subjects with T2DM, and (2) subjects with T2DM without major changes in their glycemetic control medications during the study.

Normalization of ALT and AST will be evaluated with shift tables presenting movement in and out of reference range from baseline to each scheduled post-baseline visit as defined in Section 7.9.2 and will be provided for each treatment group in the mITT population.

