7.9.2 Laboratory Evaluations

Values for the following safety laboratory tests (hematology, serum chemistry, and urinalysis) will be listed and summarized by treatment group and visit.

Hematology	Serum Chemistry	Urinalysis
Hemoglobin	Albumin*	Bilirubin
Hematocrit	Alkaline phosphatase (ALP)*	Blood
Platelets, RBC with indices	Alanine aminotransferase (ALT)*	Glucose
WBC with differential	Aspartate Aminotransferase (AST)*	Ketones
HbA1c*	Blood Urea Nitrogen (BUN)	pH
INR*	Bicarbonate	Creatinine
PT*	Calcium	Protein
	Chloride	Specific gravity
	Creatinine	Microscopic exam (if blood or protein positive)
	Fasting plasma glucose (FPG)*	
	Fasting insulin*	
	Free fatty acid (FFA)*	
	Lactate dehydrogenase (LDH)	
	Phosphorus	
	Potassium	
	Sodium	
	Gamma-Glutamyl transpeptidase (GGT)*	
	Total Bilirubin*	
	Total protein	
	Uric acid	
	Cholesterol (total, HDL, LDL, VLDL)*	
	Triglycerides*	

*Also considered an efficacy parameter.

All laboratory data will be reported in International System of Units (SI).

For analysis purposes, values preceded by a “<” or a “>” sign (i.e., those below or above the limits of quantification) will be considered equal to 0.5 × the lower limit or 1.5 × the upper limit of quantification, respectively. The proportion of subjects with values below the lower limit and above the upper limits of quantification will be provided among the summary statistics.

Laboratory evaluations measured on a continuous scale will be summarized by visit using standard descriptive statistics for the SAF population. Changes from baseline will also be summarized. Summaries will be presented for log-transformed values of ALT, AST, ALP, and GGT, in addition to summaries of non-transformed values. For analysis by visit, analysis windowing as described in Section 6.1 will be used for each scheduled visit such that unscheduled visits will also be considered. For each laboratory analyte, the baseline value will be defined as last scheduled or unscheduled value collected prior to the first dose of treatment.

For hematology and serum chemistry, shift tables presenting movement in and out of reference range from baseline to each scheduled post-baseline visit will be provided for each treatment group. An additional shift table will be produced for ALT where the upper normal limit is defined as 19 U/L for women and 30 U/L for men. Corresponding shift tables (normal vs. high /

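### The exploratory liver-test ANCOVAs adjust for one pre-dose value, although a second central-laboratory value from Screening is scheduled for every subject; using both would gain a little precision at almost no cost.

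*SAP*

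**What the plan says.** **Analysis baseline.** Under SAP 6.1 the "baseline value will be defined as the last scheduled or unscheduled value collected on or prior to the date of the first dose". SAP 7.9.2 repeats the rule for laboratory analytes: "the baseline value will be defined as last scheduled or unscheduled value collected prior to the first dose of treatment". The two wordings differ slightly. Visit 1 chemistry and hematology are drawn pre-dose (Protocol Table 1, note 9), so both normally select the Visit 1 value.

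**Model.** SAP 7.8.4 covers the liver tests: "Comparisons between each active dose and placebo will be done using ANCOVA models for continuous variables, similarly as for secondary endpoints". The secondary-endpoint models in SAP 7.8.2 carry one baseline score for each outcome. SAP 7.8.4 does not name the laboratory covariate; I take it to be the single baseline value of the analyte.

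**What is collected.** Protocol Table 1 lists liver function tests under central-laboratory evaluations at Screening and at Visits 1 to 7, and Protocol 6.2.2 lists them among the Screening procedures. Table 2 includes ALT, AST, ALP, GGT, total bilirubin, albumin, PT and INR. Protocol 7.4 bases screening eligibility on central-laboratory results.

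**Efficacy sampling.** Protocol 7.5 says samples for efficacy and safety assessment "will be drawn at all visits except Screening (Table 1"). It adds: "Blood samples for analysis of liver function tests (AST, ALT, bilirubin, PT/INR, ALP, GGT and albumin) will be collected at Study Visits 1", continuing through Visit 7.

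**Monitoring baseline.** Protocol 6.5 acts on a rise in AST, ALT or total bilirubin "greater than 2 times their baseline values (mean of Screening & Visit 1"). Protocol 6.6 uses the same reference for an "increase in PT or INR > 2 times the baseline value (mean of Screening & Visit 1").

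**The concern.** Liver enzymes vary within a person from day to day. In an ANCOVA, a noisy baseline explains less of the follow-up variance than a better-measured one. Two planned central-laboratory values precede the first dose, and the protocol averages them for monitoring five analytes. The efficacy model uses only one.

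What is at stake is the width of the confidence intervals for eight liver tests, three dose-placebo comparisons and two time points. These are exploratory endpoints, but a dose-ranging Phase 2 study will look at them when it describes dose response. No bias is at issue.

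**Working it through.** **1. The plan's own figure.** The documents give no standard deviation, correlation or power for liver tests. The only power statement concerns the primary histology endpoint: 85 per arm, 39.5% against 20%, two-sided 0.05, approximately 80% (Protocol 11.1). With the pooled chi-square formula:
- pooled rate = (0.20 + 0.395)/2 = 0.2975
- SE under the null = √(2 × 0.2975 × 0.7025/85) = 0.0701
- SE under the alternative = √((0.20 × 0.80 + 0.395 × 0.605)/85) = 0.0685
- power = Φ((0.195 − 1.96 × 0.0701)/0.0685) = Φ(0.84) = 79.96%

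The stated figure reproduces. It does not depend on the liver-test baseline.

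**2. Formula.** Let r be the correlation of a pre-dose value with follow-up, and rb that of Screening with Visit 1. Take unit variances and assume that Screening and Visit 1 predict follow-up equally well. Residual variance is then
- with one baseline: V1 = 1 − r²
- with both: V2 = 1 − 2r²/(1 + rb)

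The variance cut is 1 − V2/V1. The SE inflation from using one baseline is √(V1/V2) − 1.

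**3. Results.** All correlations are assumptions.

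| rb | r | V1 | V2 | Variance cut | SE inflation |
|---|---|---|---|---|---|
| 0.9 | 0.5 | 0.750 | 0.737 | 1.8% | 0.9% |
| 0.9 | 0.7 | 0.510 | 0.484 | 5.1% | 2.6% |
| 0.8 | 0.5 | 0.750 | 0.722 | 3.7% | 1.9% |
| 0.8 | 0.6 | 0.640 | 0.600 | 6.2% | 3.3% |
| 0.8 | 0.7 | 0.510 | 0.456 | 10.7% | 5.8% |
| 0.5 | 0.5 | 0.750 | 0.667 | 11.1% | 6.1% |
| 0.7 | 0.7 | 0.510 | 0.424 | 17.0% | 9.7% |
| 0.8 | 0.8 | 0.360 | 0.289 | 19.8% | 11.6% |

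The first five rows have rb above r. That is the more plausible ordering, because Screening is at most 42 days before Visit 1 while follow-up is at 6 or 12 months. If r is only 0.3, the cut is 0.5% (rb = 0.9) to 1.7% (rb = 0.7).

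**4. Simulation check.** With 20,000 trials of 85 per arm at rb = 0.8 and r = 0.6, the treatment-effect SE was 0.1226 with one baseline and 0.1187 with the mean of two. The ratio is 1.033, as the formula gives, and both estimators were unbiased.

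**5. In terms of power.** An effect with 80% power using both values has about 79% with one at rb/r = 0.9/0.5, about 75% at 0.8/0.7, and about 71% at 0.8/0.8.

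**6. If Screening predicts follow-up less well than Visit 1.** Write r0 for the Screening-to-follow-up correlation and r1 for Visit 1 to follow-up. The variance cut is (r0 − r1·rb)²/((1 − r1²)(1 − rb²)). With r1 = 0.6 and rb = 0.8, the denominator is 0.64 × 0.36 = 0.2304.
- r0 = 0.60: 0.12²/0.2304 = 6.2%, as in the table
- r0 = 0.54: 0.06²/0.2304 = 1.6%
- r0 = 0.6 × 0.8 = 0.48: zero

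**The case against.** **A protocol conflict.** A reader might infer that the protocol defines the liver-test baseline as a two-value mean and that the SAP abandons it. The documents do not support this. The mean appears only in Protocol 6.5 and 6.6, as the reference for on-study triggers, and only for AST, ALT, total bilirubin, PT and INR. No part of Protocol Section 11 adopts it. Protocol 7.5 lists efficacy liver-test samples from Visit 1, which agrees with the SAP rule. There is no departure, and SAP Section 8 has nothing to declare on it.

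**Wider interim intervals.** This too might be inferred, but it cannot be shown. SAP 7.10 plans descriptive statistics and defers to a separate interim SAP that is not among the documents. Protocol 11.3.4 mentions methods similar to those for the secondary mean changes, but the interim baseline rule is not visible.

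**The single value is defensible.** The last pre-dose value is a clear, prespecified baseline. The endpoints are exploratory, with no alpha or power attached. This stands, and it makes the point a suggestion rather than a correction.

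**Screening values are selected.** Upper limits on AST, ALT, bilirubin and INR exclude subjects, AST of at least 20 U/L is required before a Screening biopsy, and re-testing within Screening is allowed. Screening and Visit 1 may therefore not be interchangeable. This stands against the formula's symmetry assumption and may shrink the gain, as step 6 shows. It is also a reason to keep Visit 1 as the reference for reported change and not to average. It introduces no bias, because both values precede treatment, and separate covariates need no interchangeability.

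**Other covariates.** The formula ignores age, sex, diabetes, vitamin E use and fibrosis stage, which the secondary models include. This stands as a further limit on the figures.

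**Conclusion.** The point holds as a small, unused precision gain on exploratory endpoints. With r between 0.5 and 0.7 and the two pre-dose values more closely correlated with each other than with follow-up, adding Screening cuts residual variance by about 2-11%. Equivalently, a single baseline inflates the SE by about 1-6%. The larger cuts, from 11% up to about 20%, require Screening and Visit 1 to be no closer to each other than baseline is to follow-up, and should not be the headline.

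All of this rests on assumed correlations, on Screening and Visit 1 predicting follow-up about equally well, and on reading SAP 7.8.4 as a single-baseline ANCOVA. If Screening adds nothing beyond Visit 1, the gain is nil. For ALP, GGT and albumin the case rests on efficiency alone, since Protocol 6.5 and 6.6 do not mention them. The primary analysis, the sample size and the protocol's monitoring rules are unaffected.

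**What to change.** Add to SAP 7.8.4, before unblinding for the final analysis:

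- For ALT, AST, ALP, GGT, bilirubin, albumin, PT and INR, keep change from the last pre-dose value as the reported outcome.
- Adjust each ANCOVA for the Screening value and the Visit 1 value as two separate covariates, on the log scale where the outcome is log-transformed.
- Where Screening tests were repeated, use the last Screening-period value.
- State a rule for a missing Screening value, for example substituting the subject's Visit 1 value in every arm.

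Do the same in the interim SAP if it fits ANCOVA models. Because the Visit 1 value stays in the model, analysing change or the follow-up value gives the same treatment estimate, so the tables keep their familiar form.

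The cost is a few sentences, slightly more programming and one degree of freedom. The 340 planned completers and about 10 model terms leave roughly 330 residual degrees of freedom, so that costs about 1/330, or 0.3% of variance. No new data are needed.
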